### Rationale for Dose Selection in Part B

Prior to the transition from Part A to Part B, verification of PK model assumptions is planned as AMG 986 human PK data become available from individual IV and oral single dose cohort escalations in Part A. The IV dose regimen proposed for Part B of the study will include multiple 24 hour infusions administered for 4 consecutive days at a starting dose of 6 mg over 1 hour (LD) plus 38 mg/ 24 hours (MD; 1.57 mg/h, 36 mg/ 23 h on Day 1 and 38 mg/ 24 h on Days 2-4). A second IV cohort is proposed at 60 mg over 1 hour (LD) plus 376 mg/ 24 hours (MD; 15.7 mg/h, 360 mg/ 23 h on Day 1 and 376 mg/ 24 h on Days 2-4). The proposed once-daily (QD) oral dose regimen for Part B will be 5, 30, 100, 200, 400, and 650 mg QD for 7 consecutive days.

After confirmation of safety and tolerability of oral AMG 986 at doses that range from 5 to 200 mg in Parts A and B, further escalations in dose are planned. The proposed multiple oral dose regimen extended for Part B will be 400 mg QD and 650 mg QD for 7 consecutive days.

The planned dose escalation schedules for Part B may be modified based on treatment-emergent data (Part A or Part B safety and/or PK data). Dose adjustments, if

Approved

any, will be made for a full treatment cohort and not on an individual basis. Any dose adjustments will be agreed upon by Amgen in coordination with the investigator(s).

### **Rationale for Dose Selection in Part C**

The starting dose of 10 mg by oral route daily in Part C was based on:

- Safety and tolerability observed with an up to 200 mg single oral dose in healthy subjects, as described in the Risk Assessment section (2.3).
- Pharmacodynamic response (change in stroke volume) measured (by echocardiography) at the 5 mg and 30 mg oral single and multiple doses in healthy volunteers.

In order to evaluate a potential effect of AMG 986 in patient subjects with heart failure, a starting dose of 10 mg has been proposed that is considered safe and could also potentially be sufficient to elicit a pharmacodynamic response by echocardiography.

Prior to the transition from Part B to Part C, verification of the safety, tolerability and PK model assumptions are planned as data become available from individual IV and oral multiple dose cohort escalations in Part B. Subjects will receive AMG 986 by oral administration at a dose of 10 mg daily for the first 7 days followed by 30 mg daily for the next 7 days and ending with 100 mg daily for the last 7 days.

The planned dose schedules for Part C may be modified based on treatment-emergent data (Part A or Part B safety and/or PK data). Pre-dosing adjustments, if any, will be made for a full treatment cohort and not on an individual basis. Any dose adjustments will be agreed upon by Amgen in coordination with the investigator(s).

## **2.8 Clinical Hypotheses**

AMG 986 will be safe and well tolerated in healthy subjects and in heart failure patients after single and multiple dosing by IV infusion and oral administration.

## **3. EXPERIMENTAL PLAN**

### **3.1 Study Design**

This study is a randomized, placebo-controlled, double-blind, single day (Part A) and multiple daily (Part B) ascending dose study in healthy male and female adult subjects, between 18 and 55 years of age. Subjects will receive AMG 986 by IV infusion or by oral administration. In Parts A and B of the study, healthy subjects will receive investigational product in a fasted state. In Part C of the study, patients between the ages of 18 to 85 years with heart failure and either reduced (HFrEF) or preserved (HFpEF) ejection fraction will receive ascending doses of IP by once daily oral

administration for 21 days. The overall study design is described by a [study schema](#) at the end of the protocol synopsis section. The study endpoints are defined in [Section 10.1.1](#).

At the conclusion of each cohort, a DLRM will convene to review all available data in an unblinded fashion in order to evaluate AMG 986 safety and tolerability before advancing to the next dose cohort. In support of escalation to the next planned dose level, a review of AMG 986 exposure and dose predictions will be conducted using available PK data from all dose cohorts.

Based on emerging safety and tolerability data and upon assessment by the DLRM members, cohorts may be removed or additional cohorts may be added. Subject numbers within each cohort may also be increased or decreased based on the decision from the DLRM. Doses to be administered within each cohort may be higher or lower than the last. Dosing of any subject shall not exceed the highest planned IV and PO cohorts for Parts A and B. (Refer to [Table 7](#)).

#### **Part A.**

Part A will consist of 5 IV infusion dose cohorts and 6 PO dose cohorts. Within each cohort, a total of 8 subjects will be randomized to receive AMG 986 or placebo in a 3:1 ratio. Subjects of IV dose cohorts will be in residence for at least 48 hours. Subjects of PO dose cohorts will be in residence for at least 24 hours.

IV dosing will occur by an infusion lasting 24 hours. Infusions will be divided into an initial loading dose for the first hour followed immediately by a maintenance dose for the remainder. Subjects in the first two IV dose cohorts will receive a loading dose only with no maintenance dose. Subjects in the oral dose cohorts will receive AMG 986 as a single oral administration. The sequence of escalation for IV dosing and PO dosing will partially overlap to achieve step-wise increases in AMG 986 exposure.

In Part A of the study, AMG 986 safety and tolerability will be evaluated at an unblinded DLRM before advancing to the next dose cohort. In support of escalation to the next planned dose level, a review of AMG 986 exposure and dose predictions will be conducted using available PK data from all dose cohorts. At the conclusion of each cohort, predictions of exposure and dose will be reviewed using PK data from the most recent cohort. A review of AMG 986 safety and tolerability will adhere to these guidelines during each DLRM governing dose escalations in Part A beginning with the

starting dose cohort (cohort 1 IV, 0.5 mg) through cohort 5 IV (60 mg LD + 360 mg MD), as shown in the [study schema](#) at the end of the protocol synopsis section.

Dose escalations in Part A will initially be sequential, with AMG 986 dosing to begin at the starting IV dose of 0.5 mg infused over 1 hour, followed by escalation to IV cohort 2 dosing at 3 mg infused over 1 hour. After the safety and tolerability of AMG 986 in IV Cohort 2 are demonstrated and reviewed at a DLRM, escalation to IV Cohort 3 and initiation of oral dosing at the proposed 5 mg starting dose will be permitted.

After the safety and tolerability of AMG 986 in IV Cohort 4 (20 mg LD + 120 mg MD) is demonstrated and reviewed at a DLRM, escalation to IV Cohort 5 (60 mg LD + 360 mg MD) will be permitted. After the safety and tolerability of AMG 986 in PO Cohort 4 (200 mg) is demonstrated and reviewed at a DLRM, escalation to PO Cohort 5 (400 mg) will be permitted. Enrollment for IV Cohorts will end after IV Cohort 5. After the safety and tolerability of AMG 986 (at 400 mg) are demonstrated and reviewed at a DLRM, escalation to PO Cohort 6 (650 mg) will be permitted.

**Table 4. Intravenous Infusion and Oral Dose Escalations for Part A**

Cohort	Intravenous Infusion (up to 24 hours)		Oral Administration (single dose)	
	LD (mg/1 hour)	MD (mg/23 hours)	Cohort	Dose (mg)
Cohort 1 IV (Part A)	0.5	0	Cohort 1 PO (Part A)	5
Cohort 2 IV (Part A)	3	0	Cohort 2 PO (Part A)	30
Cohort 3 IV (Part A)	6	36	Cohort 3 PO (Part A)	100
Cohort 4 IV (Part A)	20	120	Cohort 4 PO (Part A)	200
Cohort 5 IV (Part A)	60	360	Cohort 5 PO (Part A)	400
			Cohort 6 PO (Part A)	650

The safety and tolerability of each dose level (including the final IV and PO dose cohorts) in Part A will be assessed after all subjects have been enrolled and followed through at least for 4 days post dose.

**Part B.**

Part B will consist of 2 IV infusion dose cohorts and 6 PO dose cohorts. Within each cohort, a total of 8 subjects will be randomized to receive AMG 986 or placebo in a 3:1 ratio.

In Part B of the study, AMG 986 safety and tolerability will be evaluated at a DLRM before advancing to the next dose cohort. In support of escalation to the next planned dose level, AMG 986 exposure and dose predictions will be updated using available PK data that will include observed PK exposure after single day dosing in Part A of the study. Predictions of AMG 986 exposure anticipated for cohort 2 IV (60 mg LD + 360 mg/ 23 hours MD on Day 1 and 376 mg/24 hours MD on Days 2-4) will be reviewed using available PK data from cohort 1 IV (6 mg LD + 36 mg/ 23 hours MD on Day 1 and 38 mg/24 hours MD on Days 2-4).

In the IV cohorts, AMG 986 will be dosed as a series of IV infusions, each with duration of 24 hours, for 4 consecutive days. Subjects of the IV dose cohorts will be in residence for up to 24 hours after the completion of IV infusions. On study Day 1, IV infusions will be divided into an initial loading dose infusion for 1 hour followed immediately by a maintenance dose with duration for 23 hours. On study days 2 to 4, maintenance doses will be administered as constant infusions with duration for 24 hours.

The transition from ascending single day doses in Part A to ascending multiple daily doses in Part B is planned to occur after confirmation of AMG 986 safety and tolerability in IV Cohort 4 of Part A. The starting IV dose in Part B at 6 mg (LD) + 36 mg/ 23 hours MD on Day 1 and 38 mg/24 hours MD on Days 2-4 will have been previously evaluated over 24 hours in IV Cohort 3 of Part A. The rationale for an earlier partial overlap between IV dose cohorts in Parts A and B is supported by the anticipated exposure, safety and tolerability of AMG 986 in IV Cohort 4 of Part A at 20 mg (LD) + 120 mg (MD).

In the PO cohorts, AMG 986 will be dosed once daily for 7 consecutive days. Subjects of the PO dose cohorts will be in residence for at least 24 hours after the completion of the last dose on day 7.

Parts A and B will partially overlap for the oral dose cohorts. Transition to the first PO cohorts of Part B (5 mg QD) is planned to occur upon a DLRM decision to proceed after the 30 mg PO single dose cohort in Part A has been made. Subsequent oral dose escalations to 200 mg QD will occur in Part B as shown in the [study schema](#). Escalation to 400 mg QD in Part B will be allowed after the safety and tolerability of AMG 986 at both 400 and 650 mg in Part A (PO cohorts 5 and 6, respectively) are demonstrated and reviewed at each DLRM.

Approved

**Table 5. Intravenous Infusion and Oral Dose Escalations for Part B**

Cohort	Intravenous Infusion (for 4 days)		Oral Administration (once daily for 7 days)	
	Day 1 LD (mg/1 hour)	MD (mg/24 hours)	Cohort	Dose (mg)
Cohort 1 IV (Part B)	6	38 a	Cohort 1 PO (Part B)	5
Cohort 2 IV (Part B)	60	376 b	Cohort 2 PO (Part B)	30
			Cohort 3 PO (Part B)	100
			Cohort 4 PO (Part B)	200
			Cohort 5 PO (Part B)	400
			Cohort 6 PO (Part B)	650

**a. Cohort 1 IV (Part B)**

LD: 6 mg / 1 h  
 MD: 36 mg / 23h (Day 1)  
 MD: 38 mg / 24h (Days 2-4)  
 [total infusion = 96 h]

**b. Cohort 2 IV (Part B)**

LD: 60 mg / 1 h  
 MD: 360 mg / 23h (Day 1)  
 MD: 376 mg / 24h (Days 2-4)  
 [total infusion = 96 h]

The safety and tolerability of each dose level (including the final IV and PO dose cohorts) in Part B will be assessed after all subjects have been enrolled and followed through at least 4 days post dose.

**Part C.**

Part C will consist of 2 PO dose cohorts, one cohort for HFrEF patients and one cohort for HFpEF patients. Within each cohort, 20 subjects will be randomized to receive AMG 986 or placebo in a 3:1 ratio. Subjects will receive AMG 986 by oral administration at a dose of 10 mg daily for the first 7 days followed by 30 mg daily for the next 7 days and ending with 100 mg daily for the last 7 days for a total of 21 days of treatment. In Part C of the study, AMG 986 safety and tolerability will be evaluated at the end of the 21 day dosing period in an unblinded DLRM.

**Table 6. Dose Regimen for HFrEF and HFpEF Patient Subjects in Part C**

Day(s)	Route	AMG 986 Dose
1-7	PO	10 mg daily
8-14	PO	30 mg daily
15-21	PO	100 mg daily

### **3.2 Number of Sites**

This study will be conducted in 15 or more sites in the United States, Europe, Canada and Asia. Additional sites and/or countries could be added as necessary to complete enrollment.

### **3.3 Number of Subjects**

Participants in this clinical investigation shall be referred to as “subjects”.

Approximately 152 healthy volunteer subjects and 40 heart failure patient subjects will be enrolled into the study. In Part A PO Dose Cohorts, 8 subjects per cohort will be enrolled for a total of 48 subjects across 6 cohorts. In Part A IV Dose Cohorts, 8 subjects per cohort will be enrolled for a total of 40 subjects across 5 cohorts. In Part B PO Dose Cohorts, 8 subjects per cohort will be enrolled for a total of 48 subjects across 6 cohorts. In Part B IV Dose Cohorts, 8 subjects per cohort will be enrolled for a total of 16 subjects across 2 cohorts. In Part C, up to 20 HFReEF patient subjects and up to 20 HFpEF patient subjects will be enrolled.

- Part A IV Dose Cohorts: 40 subjects (8 subjects per cohort)
- Part A PO Dose Cohorts: 48 subjects (8 subjects per cohort)
- Part B IV Dose Cohorts: 16 subjects (8 subjects per cohort)
- Part B PO Dose Cohorts: 48 subjects (8 subjects per cohort)
- Part C HFReEF cohort: Up to 20 HF patient subjects
- Part C HFpEF cohort: Up to 20 HF patient subjects

### **3.4 Replacement of Subjects**

Subjects who are withdrawn or removed from treatment or the study prior to receiving AMG 986 will be replaced at the discretion of the Amgen Medical Monitor and Principal Investigator. Subjects who are withdrawn or removed from treatment or the study may be replaced. This decision will be made by the Amgen Medical Monitor in consultation with the Principal Investigator and the Amgen Global Safety Officer.

The new subject will receive the identical treatment as the replaced subject, but will be assigned a replacement randomization number associated with this new record.

### **3.5 Estimated Study Duration**

#### **3.5.1 Study Duration for Subjects**

For both healthy volunteer subjects and heart failure patient subjects, the planned length of participation in the study is approximately 58 days, which includes a 28 day screening period followed by 30 days on study.

Approved

### 3.5.2 End of Study

The EOS is the last planned clinic visit for each subject enrolled in this study, which is at Day 30.

Primary Completion: the time when the last subject is assessed or receives an intervention for the purposes of final collection of data for the primary analysis;

End of Trial: the time when the last subject is assessed or receives an intervention for evaluation in the study.

## 4. SUBJECT ELIGIBILITY

Before any study-specific activities/procedure, the appropriate written informed consent must be obtained (see [Section 11.1](#)).

### 4.1 Inclusion Criteria

- 101 Subject has provided informed consent prior to initiation of any study-specific activities/procedures.
- 102 Male and female subjects  $\geq 18$  to  $\leq 55$  years old with no history or evidence of clinically relevant medical disorders as determined by the investigator and the Amgen physician (Parts A and B only)
- 103 Body mass index (BMI) between 18 and 35 kg/m^2, inclusive, at screening.
- 104 Physical examination including vital signs, clinical laboratory values, and ECGs are clinically acceptable to the investigator. Abnormal findings for healthy volunteers and unexpected findings for heart failure patient subjects will be discussed with Amgen prior to study enrollment.
- 105 Women must be of non-reproductive potential (ie, postmenopausal)
1. Age of  $\geq 55$  years with no menses for at least 12 months OR
  2. Age of  $< 55$  years with no menses for at least 12 months AND with postmenopausal gonadotropin levels (follicle-stimulating hormone levels  $> 40$  IU/L or according to the definition of “postmenopausal range” for the laboratory involved) OR
  3. History of hysterectomy OR
  4. History of bilateral oophorectomy.
- 106 Men must agree to practice an acceptable method of effective birth control while on study through 11 weeks after receiving the last dose of investigational product (AMG 986 or placebo). Acceptable methods of effective birth control include sexual abstinence; vasectomy and testing that shows there are no sperm in the semen; or a condom with spermicide (men) in combination with barrier methods (diaphragm, cervical cap or cervical sponge), hormonal birth control or IUS (women).

Approved

- 107 Men must be willing to abstain from sperm donation while on study through 11 weeks after receiving the last dose of investigational product (AMG 986 or placebo).
- 108 This inclusion criterion only applies to Parts B and C cohorts. Before inclusion in the study, subjects will undergo a screening echocardiogram to ensure that the following parameters can be accurately measured: left ventricular end-systolic and end-diastolic volumes, left atrial end-systolic and end-diastolic volumes, ejection fraction, fraction shortening, and end-systolic septal and posterior wall thickness.

For Part C

Additional Inclusion Criteria for HFrEF Patients

- 109 Subject must be of age 18 to 85 years, have a diagnosis of HF confirmed by medical records for  $\geq 3$  months, and be in stable condition for at least 4 weeks.
- 110 Left ventricular ejection fraction (LVEF)  $\leq 40\%$  confirmed by echocardiogram, radionuclide ventriculography, cardiac magnetic resonance imaging, or contrast ventriculography within 12 months prior to randomization.
- 111 NYHA class II or III at screening
- 112 Sinus rhythm
- 113 NT-proBNP level  $\geq 250$  pg/ml
- 114 Patients will be treated with stable, optimal pharmacological therapy for a minimum of 4 weeks prior to randomization. Treatment of HFrEF includes at least beta-blockers (carvedilol, metoprolol succinate or bisoprolol) and a RAAS inhibitor (ACEi, ARB or sacubitril/valsartan).

Additional Inclusion Criteria for HFpEF patients

- 115 Subject must be of age of 18 to 85 years, have a diagnosis of HF confirmed by medical records for  $\geq 3$  months, and be in stable condition for at least 4 weeks.
- 116 Left ventricular ejection fraction (LVEF)  $\geq 50\%$  confirmed by echocardiogram, radionuclide ventriculography, cardiac magnetic resonance imaging, or contrast ventriculography within 12 months prior to randomization.
- 117 Left ventricular ejection fraction (LVEF) never  $\leq 40\%$  in the past
- 118 NYHA class II or III at screening
- 119 Sinus rhythm
- 120 NT-proBNP level  $\geq 250$  pg/ml

Approved

- 121 Patients will be treated with stable, optimal pharmacological therapy for a minimum of 4 weeks prior to randomization. Treatment of HFpEF includes at least a daily dose of diuretics equivalent to furosemide 40 mg.
- 122 For subjects in Parts A, B and C: Women must have negative results for both the screening (serum) and day -1 (serum or urine) pregnancy tests

#### 4.2 Exclusion Criteria

- 201 Currently receiving treatment in another investigational device or drug study, or less than 30 days or 5 half-lives (whichever is longer), since ending treatment on another investigational device or drug study(s) prior to receiving the first dose of investigational product (AMG 986 or placebo).
- 202 Female subjects who are lactating/breastfeeding or who plan to breastfeed while on study through 11 weeks after receiving the last dose of investigational product (AMG 986 or placebo).
- 203 Male subjects with partners who are pregnant or planning to become pregnant while the subject is on study through 11 weeks after receiving the last dose of investigational product (AMG 986 or placebo).
- 204 Female subjects of reproductive potential.
- 205 Subjects in Parts A and B of the study: estimated glomerular filtration rate (eGFR) within the screening period of less than 60 mL/min/1.73m^2 as calculated using the estimated Modification of Diet in Renal Disease (MDRD) formula.
- 206 Current or prior malignancy within 5 years of randomization, with the exception of non-melanoma skin cancers, cervical or breast ductal carcinoma in situ, and adenocarcinoma of the prostate Stage I or IIa (defined as T1, T2a or T2b, N0, M0 with documented serum PSA < 20 ng/mL and Gleason score ≤ 7) per the American Joint Committee on Cancer (AJCC) primary tumor, regional lymph nodes, and distant metastasis system.
- 207 Positive results for Human Immunodeficiency Virus (HIV), antibodies, hepatitis B surface antigen (HBsAg), or hepatitis C antibodies (HepCAb).
- 208 Subject has known sensitivity to any of the products or components to be administered during dosing.
- 209 Subject likely to not be available to complete all protocol-required study visits or procedures, and/or to comply with all required study procedures to the best of the subject and investigator's knowledge.
- 210 History or evidence of any other clinically significant disorder, condition or disease with the exception of those outlined above that, in the opinion of the investigator or Amgen physician, if consulted, would pose a risk to subject safety or interfere with the study evaluation, procedures or completion.
- 211 Subject previously has entered this study or has been previously exposed to AMG 986.

Approved

- 212 Concurrent or prior use of strong CYP3A4 inhibitors within 14 days of study Day 1, including (not limited to): macrolide antibiotics (eg, clarithromycin, telithromycin), antifungals (eg, itraconazole, voriconazole), antivirals (eg, ritonavir, saquinavir, indinavir, nelfinavir), nefazodone.
- 213 Concurrent or prior ingestion of grapefruit or grapefruit products and other foods that are known to inhibit CYP3A4 within 7 days of study Day 1.
- 214 Concurrent or prior use of strong CYP3A4 inducers within 28 days of study Day 1, including (not limited to): phenytoin, carbamazepine, rifampin, rifabutin, rifapentin, phenobarbital. Subjects should also not take St John's Wort.
- 215 Concurrent or prior use of strong P-glycoprotein inhibitors within 28 days of study Day 1, including (not limited to): elacridar and valsopodar.
- 216 All herbal supplements, vitamins, and nutritional supplements taken within the last 30 days prior to dosing on Day 1 (and continued use, if appropriate), must be reviewed and approved by the PI and Amgen Medical Monitor.
- 217 For subjects enrolled under Amendments 1-6, inclusive: QTc > 450 msec or history/evidence of long QT syndrome.
- 218 Planned elective surgery within 30 days of study completion or before return of red blood cell parameters to normal values.
- 219 Blood donation  $\geq$  500 mL within 60 days of Day 1.
- 220 Systolic blood pressure > 150 mm Hg or < 90 mm Hg, or diastolic blood pressure > 95 mm Hg or < 60 mm Hg, assessed on 2 separate occasions prior to enrollment (Parts A and B only).
- 221 Heart rate  $\geq$  100 beats per minute after 5 minutes of rest or an untreated symptomatic bradyarrhythmia within 1 month prior to enrollment.
- 222 **For Parts A and B:** Troponin I at screening > upper limit of normal (ULN).
- 223 In the opinion of the Investigator, a condition that compromises the ability of the subject to give written informed consent or to comply with study procedures.
- 224 Unwilling or unable to abstain from nicotine or tobacco containing products (including but not limited to: snuff, chewing tobacco, cigars, cigarettes, pipes, or nicotine patches) throughout the screening period and for the duration of the study.
- 225 Subjects who are unwilling or unable to limit alcohol consumption to 1 units/day (1 unit = 1 drink and 1 drink is equivalent to 12 ounces of regular beer, 8 to 9 ounces of malt liquor, 5 ounces of wine or 1.5 ounces of 80 proof distilled spirits).
- 226 Subjects with a positive urine drug screen or alcohol breath test.
- 227 Known history of drug or alcohol abuse.
- 228 Concurrent use of Phosphodiesterase 5 (PDE5) inhibitors including (not limited to) avanafil, sildenafil, tadalafil, vardenafil.

Approved

- 229 Concurrent use of vasodilators by healthy subjects in Parts A and B that could in the opinion of the investigator potentially lead to a drop in blood pressure in combination with investigational product.
- 230 Severe uncorrected valvular heart disease, or hypertrophic obstructive cardiomyopathy, active myocarditis, constrictive pericarditis, or clinically significant congenital heart disease.
- 231 For subjects in Part C of the study: estimated glomerular filtration rate (eGFR) within the screening period of less than 30 mL/min/1.732m^2 as calculated using the Modification of Diet in Renal Disease (MDRD) formula.
- 232 For subjects in Part C of the study: Systolic blood pressure > 160 mm Hg or < 100 mm Hg, or diastolic blood pressure > 110 mm Hg or < 60 mm Hg, assessed on 2 separate occasions prior to enrollment.
- 233 For subjects in Part C of the study: Troponin I > ULN if there is also evidence of an acute cardiovascular event.
- 234 For subjects enrolled in Part C under Amendment 7: QTc > 500 msec or history/evidence of long QT syndrome.

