If the investigator has any questions regarding a subject's eligibility, he/she should contact the Amgen Medical Monitor. The site is to document the enrollment date in the subject's medical record and the electronic case report form (CRF).

Rescreening will be allowed for this study on a case-by-case basis at the discretion of the Amgen Medical Monitor in consultation with the Principal Investigator.

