**5. Breast Feeding Information**

Did the mother breastfeed or provide the infant with pumped breast milk while actively taking an Amgen product?  Yes  No  
If No, provide stop date: mm \_\_\_\_ / dd \_\_\_\_ / yyyy \_\_\_\_  
Infant date of birth: mm \_\_\_\_ / dd \_\_\_\_ / yyyy \_\_\_\_  
Infant gender:  Female  Male  
Is the infant healthy?  Yes  No  Unknown  N/A

If any Adverse Event was experienced by the mother or the infant, provide brief details: \_\_\_\_\_  
\_\_\_\_\_  
\_\_\_\_\_

Form Completed by:  
Print Name: \_\_\_\_\_ Title: \_\_\_\_\_  
Signature: \_\_\_\_\_ Date: \_\_\_\_\_

Approved

## Protocol Amendment 8

**Title: A Phase I, Randomized, Double-Blind, Placebo-Controlled, Single and Multiple Ascending Dose Study to Evaluate the Safety, Tolerability, Pharmacokinetics and Pharmacodynamics of AMG 986 in Healthy Subjects and Heart Failure Patients**

Amgen Protocol Number (AMG 986) 20150183

IND Number 129185

Eudra-CT 2017-002940-34

Amendment Date: 27 July 2018

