## 1. Introduction

The purpose of this Statistical Analysis Plan (SAP) is to provide details of the statistical analyses that have been outlined within the Protocol Amendment 8 for Study 20150183 AMG 986 dated 27 July 2018. The scope of this plan includes the primary analysis that is planned and will be executed by the Biostatistics department unless otherwise specified. **The scope of the analysis is restricted post the discontinuation of the study earlier than planned and includes key analyses to be performed as identified by the study team.**

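### Minor, probably a drafting slip: read literally, no numeric QTc entry limit or named long-QT exclusion covers Part C patients enrolled under the current Amendment 8

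*Protocol*

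**What the plan says.** Two numbered exclusions in Protocol Section 4.2 deal with the QT interval.

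- Item 217: "For subjects enrolled under Amendments 1-6, inclusive: QTc > 450 msec or history/evidence of long QT syndrome".
- Item 234: "For subjects enrolled in Part C under Amendment 7: QTc > 500 msec or history/evidence of long QT syndrome".

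The other exclusions written only for Part C (items 231, 232 and 233) are tied to the study part and not to an amendment. Item 233, for example, reads "For subjects in Part C of the study: Troponin I > ULN if there is also evidence of an acute cardiovascular event".

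The current protocol is Amendment 8. Its title block gives "Amendment Date: 27 July 2018", and SAP Section 1 says that it details the analyses outlined in "Protocol Amendment 8 for Study 20150183 AMG 986 dated 27 July 2018".

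Three general provisions also bear on entry.

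- Inclusion 104 requires an ECG that the investigator finds clinically acceptable, and adds: "Abnormal findings for healthy volunteers and unexpected findings for heart failure patient subjects will be discussed with Amgen prior to study enrollment".
- Exclusion 210 removes anyone with another significant condition that, "in the opinion of the investigator or Amgen physician, if consulted, would pose a risk to subject safety" or would interfere with the study.
- Section 5 says: "If the investigator has any questions regarding a subject's eligibility, he/she should contact the Amgen Medical Monitor".

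**The concern.** Both QTc exclusions are scoped by amendment number, and neither scope includes Amendment 8. A site that applies the criteria exactly as printed to a Part C patient enrolled under Amendment 8 finds no numeric QTc limit and no exclusion that names long QT syndrome. A stated safety threshold has become a matter of judgement, apparently by accident.

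What is at stake is the clarity of an entry rule for patients with heart failure. No estimate, test or sample-size figure depends on it.

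**Working it through.** No power or alpha calculation applies. The check compares the literal scope of each QTc entry statement with the group being enrolled.

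**Coverage by amendment**

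| Enrolled under | Item 217 (450 msec) | Item 234 (500 msec) | ECG footnote C, Tables 9 to 13 (450 msec) |
|---|---|---|---|
| Amendments 1 to 6 | applies | no | Parts A and B only |
| Amendment 7, Part C | no | applies | no |
| Amendment 8, Part C | no | no | no |

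Footnote C is the only other QTc eligibility text. It belongs to the Part A and B schedules. Part C has its own schedule, Table 14, whose ECG footnote (B) sets no threshold.

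**How unusual the scoping is**

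- Inclusion criteria: 122 − 101 + 1 = 22. Exclusion criteria: 234 − 201 + 1 = 34. Total: 22 + 34 = 56.
- Criteria naming QTc or long QT: 2 of 56 (217 and 234).
- Criteria limited by amendment: 2 of 56, the same two.
- Exclusions specific to Part C: 4 (231 to 234), of which only 234 carries an amendment limit.

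These counts show where the wording departs from its neighbours. They do not measure an effect.

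**Who could be affected**

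- Planned healthy cohorts: Part A 5 + 6 = 11, Part B 2 + 6 = 8, total 19. Section 2.4.1 reports 19 healthy cohorts fully implemented as of 01 June 2018, before Amendment 8. Unless cohorts were added, enrollment under Amendment 8 is Part C only.
- Part C was planned for up to 40 patients (Section 3.3). Data from 12 had been reviewed by 01 June 2018 (Section 2.4.1), so those 12 were enrolled before Amendment 8.
- Largest possible number under Amendment 8, if Part C kept to its planned maximum: 40 − 12 = 28. Smallest: 0. The documents do not say where in 0 to 28 the number lies.

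**Intent**

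The Amendment 7 rationale describes a plain extension of the QTc threshold from 450 to 500 msec, supported by nonclinical and healthy-volunteer findings, with no end date. The Amendment 8 rationale is alignment with the Investigator's Brochure and correction of inconsistencies and typographical errors. Its listed changes, as visible in the public document, include none to Section 4.2. The simplest explanation is that item 234 was carried forward without updating its scope.

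**The case against.** The strongest reply is that no reader would be misled. Item 234 is still printed as the only QTc exclusion for Part C, and a sensible site would go on applying 500 msec. That is probably what happened. It does not settle the literal scope, because item 217 uses an explicit closed range of amendments. Next to it, a bare reference to Amendment 7 does not naturally mean Amendment 7 onward.

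A reader might go further than the gap itself. Four such inferences are not supported.

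- **That patients were left unprotected.** Inclusion 104, exclusion 210 and the Medical Monitor route all remain at entry. After dosing, Table 8 has a QTc rule with no amendment limit: a confirmed value of 500 msec or more, or a rise of 60 msec or more, stops dosing for the subject and leads to electrolyte checks, hourly ECGs and a dose level review. Part C Day 1 ECGs at 1, 2, 4 and 6 hours fall within its 6-hour window. Two limits remain: its trigger wording refers to 2 subjects in the cohort, and it acts only once drug has been given.
- **That the reporting would hide such patients.** SAP Section 11 drops subject-level ECG listings, so an individual's QTc would not be itemised. However, SAP Section 10.4 still presents medical history for each subject, where a recorded long QT history would appear. SAP Section 10.5.5 still summarises ECG parameters by treatment group within each Part C cohort, and Section 10.1 includes ranges, so an extreme recorded baseline QTc should show as a maximum. (Protocol Section 10.5.2.1.3 had not planned Part C ECG summaries; I take the later SAP as governing.)
- **That the sponsor meant to drop the limit.** Nothing in either amendment rationale says so.
- **That there is a demonstrated QT hazard.** The protocol reports no QTc effect in the dog studies and, in the Amendment 7 rationale, no evidence of one in Parts A and B.

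**Conclusion.** The gap is real on the face of the current criteria, and it is minor. For Part C patients enrolled under Amendment 8, the printed exclusions contain no numeric QTc entry limit and do not name long QT syndrome. The judgement-based entry provisions and the Table 8 rule reduce the practical risk. Neither is a substitute for a stated entry threshold.

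This rests on a literal reading of items 217 and 234, and on Tables 9 to 13 footnote C not extending to Part C. The range of 0 to 28 assumes that Part C did not exceed 40 patients. No wrongly enrolled or harmed patient is shown. The SAP version history cites a discontinuation memo dated 15 April 2019, so the consequence may be nil.

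**What to change.** In Protocol Section 4.2, item 234, insert the words 'or later' after the reference to Amendment 7. Leave the 500 msec threshold and the long-QT wording as they are.

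The cost is two words in a clarification. No new procedure is needed, since Section 7.2.13 already requires QTc on every Part C ECG. No additional listing or analysis is proposed, given the outputs that the SAP retains. With enrollment ended early, the change matters mainly if enrollment resumes or the criterion is reused in a later protocol.
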